### **Safety Profile of rVSV $\Delta$ G-ZEBOV-GP**

Preliminary safety data collected to date have demonstrated rVSV $\Delta$ G-ZEBOV-GP to be generally well-tolerated when administered to healthy adults. Injection-site reactions following vaccination are generally mild or moderate and self-limited. Thereafter, there is a predictable period of early reactogenicity, including fever and a flu-like syndrome, which is common after receipt of other live-virus vaccines, and resolves within 7 days. During this time, transient decreases in white blood cells and platelets have also been observed but bleeding or increased risk of infection

has not been reported. The early reactogenicity is likely to be a result of viremia with the vaccine virus which has been reported in the majority of subjects and resolves within 2 weeks. Mild and self-limited oral ulcers have been observed in a few subjects. No rVSV has been detected in oral ulcers to date. Vaccine virus has been found in saliva, urine, and skin-vesicles from those vaccinated. The largest proportion of adult subjects that had vaccine virus detected in saliva or urine was 5 of 20 in  $2 \times 10^7$  pfu recipients with positive saliva on Day 7 and this decreased to 1 of 10 on Day 14. Person-to-person transmission has not been documented.

Joint pain (arthralgia) has been reported in the first week after vaccination in up to 35% of vaccinees (range 5 to 35%, blinded data). In a small proportion of subjects (<5% at most study sites), joint swelling (arthritis) has been observed in the 2nd to 3rd week after vaccination.

In one Phase 1 clinical trial in which 25 of the 51 subjects that received the study vaccine were vaccinated in an open-labeled manner because they were deployable to the Ebola outbreak, the proportion of subjects with arthritis was higher (11 of 51; 22%) for reasons that have not been fully elucidated. The arthritis is thought to be virally-mediated, and a vast majority of cases have resolved within several weeks. However, several subjects have reported recurrent or persistent arthralgia and arthritis up to 6 months of vaccination, the longest time followed to date.

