### 2.4. Secondary objectives

The following secondary objectives will be assessed. Unless otherwise stated, the objectives will be addressed separately for adults and children:

- To compare the groups given the Ad26.ZEBOV prime vaccine and the rVSVΔG-ZEBOV-GP prime vaccine (both rVSVΔG-ZEBOV-GP groups combined) each with the pooled placebo group for the antibody response 14 days after randomization (prime vaccination) (immediacy of response).
- To compare each of the vaccine groups versus the pooled placebo group for the antibody response profile using measurements at 7, 14, 28, 56, 63 days and at 3, 6 and 12 months after randomization.
- To compare each of the vaccine groups with the pooled placebo group for SAEs at 12 months (see section [4.1.3](#)).
- To compare the groups given the Ad26.ZEBOV prime vaccine and the rVSVΔG-ZEBOV-GP prime vaccine (both rVSVΔG-ZEBOV-GP groups combined) each with the pooled placebo group for the percent with injection site reactions and AEs graded for severity, including targeted symptoms, during the first week following randomization (including the daily contacts for children only).
- To compare the groups given the Ad26.ZEBOV prime vaccine and the rVSVΔG-ZEBOV-GP prime vaccine (both rVSVΔG-ZEBOV-GP groups combined) each with the pooled placebo group for percent reporting injection site reactions and AEs graded for severity, including targeted symptoms, following prime vaccination at the vaccination visit, and through 7, 14, and 28 days after the prime vaccination.

- To compare each of the vaccine groups with the pooled placebo group for changes from baseline in biochemical markers and complete blood count (CBC) measurements at 7 days after randomization (children only).
- To compare the rHAd26/MVA and rVSVΔG-ZEBOV-GP boost strategies with the pooled placebo group for changes from baseline in biochemical markers and CBC measurements at 63 days after randomization (children only).
- To compare the rHAd26/MVA and rVSVΔG-ZEBOV-GP boost strategies with the pooled placebo for percent with injection site reactions and AEs graded for severity, including targeted symptoms, immediately following the booster vaccination and through month 3 (approximately 35 days after the booster vaccination).
- To compare the three vaccine strategies versus the pooled placebo group for long-term antibody response at 24, 36, 48 and 60 months following randomization (if funding permits).

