### **3.3. Follow-up data collection**

Following randomization, all participants will be seen at the following visits (visit window): 7 ( $\pm 3$  days), 14 ( $\pm 3$  days), 28 ( $\pm 7$  days), 56 (53 to 66 days) and 63 days (7  $\pm 3$  days after the booster vaccination), and at 3 ( $\pm 14$  days), 6 ( $\pm 1$  month), and 12 ( $\pm 1$  month) months. Participants may continue to be seen at 24 ( $\pm 1$  month), 36 ( $\pm 1$  month), 48 ( $\pm 1$  month) and 60 ( $\pm 1$  month) months if funding permits.

At each follow-up visit, volunteers will be asked a few questions to assess the development of any serious medical conditions (e.g., malaria), the possibility of unreported SAEs, and for women whether they are pregnant. Temperature will be recorded, and blood will be drawn for immunogenicity testing and future research.

The following additional information will be collected at 7, 14, 28, and 63 days and at 3 months (approximately 35 days after the booster) following randomization:

- Grade 3 and 4 AEs and targeted symptoms since vaccination
- Injection site reactions since vaccination

The following additional specimens and information will be obtained for children: 1) during the first week following the prime and booster vaccination, there will be daily contacts with children to assess injection site reactions, targeted symptoms and SAEs, and to measure temperature; 2) on day 7 and 63, serum for AST, ALT, creatinine, and potassium and blood for CBC with differential, platelet count, hemoglobin, hematocrit, MCV, and RDW will be obtained; 3) on day 28, at months 3 and 6 and annually weight will be recorded; 4) annually height will be measured;

and 5) mid-upper arm circumference (children aged 1-5 years) will be measured at months 3, 6, and 12, and then annually if funding permits.

For a subsample of adults, at baseline and days 7, 14, 56, 63, 70, and month 12, cells for assessing T cell and memory B cell function will be obtained. If funding permits, cells will also be collected at 24, 36, 48 and 60 months,

On day 56 prior to the booster vaccination, a urine pregnancy test will be performed for females of child-bearing potential, i.e., females who have experienced menarche or who are aged 14 years and older. If a woman is pregnant, she cannot receive the booster vaccination. However, she will remain under follow-up.

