SAEs will be classified by system organ class according to MedDRA®. The total number of events and the number of participants with at least one event will be reported. Mantel-Haenszel chi-square statistics will be used for each pair-wise comparison of the number of participants with an SAE through 12 months of follow-up; time-to-event methods, e.g., Kaplan-Meier, Cox regression, will also be used to compare groups for SAEs over the 12 month follow-up period. Analyses will also be carried out for SAEs judged to be related to the vaccine. If follow-up is extended to 60 months, similar analyses will be performed for SAEs reported through 60 months.

Each vaccine group will be compared with the pooled placebo group using Mantel-Haenszel chi-square tests and time-to-event methods for diagnoses of laboratory-confirmed malaria through 12 months of follow-up.

For safety and efficacy outcomes assessed before the booster at 56 days, the two groups given the rVSVΔG-ZEBOV-GP prime vaccination will be combined for comparisons with pooled placebo group. For outcomes that are assessed after 56 days, each of the three vaccination strategies will be compared with the pooled placebo group.

Mantel-Haenszel chi-square tests will be used to compare each vaccine with placebo for the percent with grade 3 or 4 AEs and with targeted symptoms reported at 7, 14, and 63 days. Similar methods will be used to compare injection site reactions reported immediately following prime vaccination and at 7 and 14 days. Likewise, treatment differences in injection site reactions reported immediately following booster vaccination and through day 63 (7 days after booster vaccination) will be summarized with similar methods. In the event that there is evidence that safety outcomes differ between the two placebo groups, analyses will also be performed for each vaccine versus its matched placebo.

Longitudinal mixed models will be used to compare log-transformed antibody levels collected at multiple follow-up time points during follow-up. Results will be summarized as geometric means and geometric mean ratios. These analyses will be carried out among participants who did not have elevated antibody levels at baseline. Baseline titer level will be included as a covariate. These analyses will be supplemented with scatter plots that display fold increases in antibody titers, line plots, box plots and reverse cumulative distributions of antibody levels at each visit for each vaccine group.

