#### **2.1.5.5 Injection site reactions, targeted symptoms and grade 3 or 4 adverse events at scheduled follow-up visits following prime vaccination**

The number and percentage of participants who report an injection site reaction (any redness or swelling induration) within 30 minutes after prime vaccination (baseline), one week after prime vaccination (day 7), 2 weeks after prime vaccination (day 14), and one month after prime vaccination (day 28) will be summarized. Similarly, the number and percentage of participants who report an injection site reaction 30 minutes after booster vaccination (day 56), one week after booster vaccination (day 63), and one month after booster vaccination (month 3) will be summarized by vaccine group. For these analyses, proportions will be compared between each vaccine strategy and the pooled placebo using the Mantel Haenszel chi-square test stratified by site.

For safety outcomes, comparisons may also be made between each active vaccine and its matching placebo.

Pain/tenderness with activity, itching at injection site, and targeted symptoms are graded as not present or grade 1-4. For each of these, the number and percent of participants with each reported symptom or any of the symptoms will be summarized. For each symptom, the number and percent with each grade will also be summarized. Participants with unsolicited symptoms will be listed. The percent with fever (body temperature > 38.0 °C) will also be summarized. These summaries will be carried at the time points mentioned above. For these analyses, proportions will be compared between each vaccine strategy and the pooled placebo using the Mantel Haenszel chi-square test stratified by site. Comparisons may also be made between each active vaccine and its matching placebo.

**Note: Analyses of safety data after day 56 will be carried out on all participants, including those who did not receive the booster vaccination. As previously noted, a very high percentage of participants received the booster vaccination. Among participant who did not receive the booster, most did not complete questions concerning symptoms at Day 63 and 3 months.**

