#### **2.1.5.6 Daily diary for children**

For children, injection site reactions, targeted symptoms of any grade severity and

unsolicited grade 3 or 4 adverse events are assessed each day during the week following prime and booster vaccination. The daily diary results will be summarized as described in the previous section. In addition, the number and percent of children reporting the different events at least once will be summarized.

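### The protocol's objective is the cumulative percent with reactions and symptoms through Days 7, 14 and 28 and through Month 3, but the SAP compares percentages visit by visit and defines no ever-reported variable outside the children's diary

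*SAP*

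**What the plan says.** **The objective.** Protocol 2.4 compares each prime vaccine with pooled placebo for the percent reporting injection site reactions and graded events "following prime vaccination at the vaccination visit, and through 7, 14, and 28 days after the prime vaccination". It asks for the same after the booster, through Month 3.

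**The protocol's analysis section.** Protocol 7.1 is not uniform. It plans Mantel-Haenszel tests of the "percent with grade 3 or 4 AEs and with targeted symptoms reported at 7, 14, and 63 days", which is per-visit wording. For injection site reactions after the booster it changes to a through-Day-63 form.

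**The collection.** Protocol 3.3 lists, for the Day 7, 14, 28, 63 and Month 3 visits, "Grade 3 and 4 AEs and targeted symptoms since vaccination" and "Injection site reactions since vaccination".

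**The SAP.** Section 2.1.5.5 summarises and tests percentages within 30 minutes of the prime and then "one week after prime vaccination (day 7), 2 weeks after prime vaccination (day 14), and one month after prime vaccination (day 28", with matching points after the booster (Day 56, Day 63, Month 3). It does not say what period each visit's answer covers. A person-level ever-reported figure appears only in SAP 2.1.5.6, for the diary covering the week after each vaccination: "the number and percent of children reporting the different events at least once will be summarized".

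**The concern.** A percentage through Day 28 and a percentage reported at the Day 28 visit coincide only if every earlier report is repeated at Day 28 by a participant who attends. The SAP neither says that this is assumed nor builds a variable that would make it unnecessary. Adults get no ever-reported percentage in any window, and children get none beyond the diary week.

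The clearest case is joint symptoms after rVSV. The protocol's safety summary states that "joint swelling (arthritis) has been observed in the 2nd to 3rd week after vaccination", which straddles the Day 14 and Day 28 visits, and arthritis was the reason the rVSV arms were held back from Version 2.0. An event of this kind can be reported at Day 14 and resolve before Day 28. If it is not mentioned again, it drops out of the Day 28 percentage, which is the one a reader would take as the answer to the objective.

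**Working it through.** **1. What the Day 28 figure counts.** Let C be the true percent with at least one report through Day 28, a the share of those people who reported before the Day 28 visit, and m the share of those earlier reporters who are not counted again at Day 28. Then

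Day 28 figure = C × (1 − a × m).

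The documents give neither a nor m. With C = 5.1% (the arthritis rate of 40/790 in the phase 3 lot trial, protocol 1.1.3) and a = 0.5 (assumed):

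| m (assumed) | Day 28 figure |
|---|---|
| 0 (perfect look-back) | 5.1% |
| 0.25 | 5.1 × 0.875 = 4.46% |
| 0.5 | 5.1 × 0.75 = 3.83% |
| 1 (no overlap between visits) | 5.1 × 0.5 = 2.55% |

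**2. The plan's own safety power, as a check on the method.** No power is stated for reactions or symptoms. The nearest figure is in protocol 2.7: SAEs of 5% versus 12%, 400 per group, alpha 0.0167 two-sided, power 0.88. The formula is power = Φ[(|p1 − p2| − z × s0) / s1], where s0 is the standard error under the pooled rate and s1 the standard error under the two rates.
- Pooled rate 0.085; s0 = √(0.085 × 0.915 × 2/400) = 0.01972; s1 = √((0.0475 + 0.1056)/400) = 0.01956; z = 2.393.
- (0.07 − 2.393 × 0.01972)/0.01956 = 1.166, so power = 0.878. The stated figure is reproduced.
- The companion figure (5% versus 14%, 400 versus 200, stated 0.86) gives 0.896 without and 0.868 with a continuity correction.

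**3. Joint swelling before the booster.** In one age stratum of 1,400 with 2:1:2:1:1 allocation, rVSV has 400 + 200 = 600 and pooled placebo 200 + 200 = 400. Protocol 7.1 combines the two rVSV groups before Day 56 and tests two comparisons at 0.025 each (z = 2.241). For 5.1% versus 1% (placebo rate assumed):
- Cumulative: pooled rate (30.6 + 4)/1,000 = 0.0346; s0 = 0.01180; s1 = 0.01027; (0.041 − 2.241 × 0.01180)/0.01027 = 1.42, so power = 0.92.
- At one visit holding half the events (2.55% versus 0.5%), the same formula gives 0.59.
- Counts are small, so the formula is rough. Simulating the Mantel-Haenszel test (one stratum, no continuity correction, 40,000 runs) gives 0.95 and 0.64. Summing exact binomial probabilities gives 0.945 and 0.638.

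**4. The range.** Simulated power for an even split over two non-overlapping visits, which is the worst case m = 1:

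| rVSV vs placebo | Cumulative | One visit | Either of two visits |
|---|---|---|---|
| 5.1% vs 0% (lot trial) | 1.00 | 0.99 | 1.00 |
| 4.2% vs 0% (lot trial, higher dose) | 1.00 | 0.94 | 1.00 |
| 5.1% vs 0.5% (placebo assumed) | 0.995 | 0.84 | 0.98 |
| 5.1% vs 1% (placebo assumed) | 0.95 | 0.64 | 0.88 |
| 4.2% vs 1% (placebo assumed) | 0.82 | 0.45 | 0.70 |
| 5% vs 2% (assumed) | 0.59 | 0.27 | 0.48 |
| 4.5% vs 3.2% (phase 1b trial) | 0.10 | 0.05 | 0.10 |

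The last column gives two chances at 0.025 each, so its type 1 error is higher than that of the cumulative test. With m = 0 the Day 28 test is the cumulative test and nothing is lost. Site stratification and missed visits are ignored throughout.

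**The case against.** The strongest reply is that protocol 3.3 already reconciles the two documents. If each visit asks about everything since vaccination, the percent reporting at Day 28 is by design the percent through Day 28, and likewise at Month 3 for the booster. This largely stands. It means that a split of week 2-3 joint swelling across visits, which a reader might infer from the SAP's list of time points, is not established.

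It is also fair that the SAP did not invent the per-visit form: protocol 7.1 uses it too, so part of the inconsistency lies inside the protocol. And an ever-reported figure through Day 28 would still not match the lot trial's arthritis rates, which run to 42 days and rest on a diagnosis rather than a targeted symptom. Comparability with earlier trials is therefore not a good argument for the change.

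Three things survive the reply. The SAP does not state the look-back, and from Day 63 onwards the protocol's phrase does not say which of the two vaccinations it refers to. A look-back question cannot recover a participant who misses the later visit or does not repeat an earlier report. And the 30-minute, diary and visit reports are never brought together for one person.

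**Conclusion.** The mismatch is real but modest. The stated objective is cumulative, the planned comparison is by visit, and the variable that would answer the objective exactly is not defined. The direction is known: among participants with a Day 28 report, the single-visit percentage can only equal or fall below the cumulative one. The size is not known, because it depends on unrepeated reports and missed visits, for which the documents give no rate.

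A reader might infer that the trial loses most of its power for joint swelling. The documents do not support that. It requires setting aside the look-back in protocol 3.3 and assuming an even, non-overlapping split. Even then, one-visit power is 0.94 or higher at the lot trial's rates. It falls by about a third for 5.1% versus 1% ((0.95 − 0.64)/0.95 = 33%) and by 45% for 4.2% versus 1% ((0.82 − 0.45)/0.82). Losses of half or more need weak effects or a thinner spread of events, such as 5% versus 2% (0.59 to 0.27), or 4.2% versus 1% over three visits (0.82 to 0.25). The case for the change rests on answering the stated objective, not on a power figure.

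**What to change.** In SAP 2.1.5.5:

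1. State that visit reports look back to the most recent vaccination.
2. Add, for adults and children, the comparison that matches protocol 2.4: the percent with at least one report from the prime through Days 7, 14 and 28, and from the booster through Day 63 and Month 3. Combine the 30-minute, diary (children) and visit reports, and take the maximum grade per symptom.
3. Give a denominator rule for missed visits. For the booster windows it must also cover participants who were not boosted (1,401 − 1,325 = 76 adults and 1,401 − 1,372 = 29 children), since the SAP notes that most of them did not complete the symptom questions at Day 63 and Month 3.
4. Keep the per-visit comparisons of protocol 7.1 as supporting tables.

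The cost is a few lines of SAP text and one derived variable per symptom and window, from data already collected. The SAP says it was written before unblinding, so the definition can be fixed without knowledge of results. The only real burden is the missed-visit rule, which needs a choice and a short justification.

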**Background and Rationale:**

Preliminary data from an open-label, cluster randomized ring vaccination trial conducted in Guinea indicate that the Merck/New Link rVSVΔG-ZEBOV-GP vaccine prevented Ebola virus (EBOV) disease (EVD) events occurring at least 10 days after randomization among close contacts immediately vaccinated as

compared to those to be potentially vaccinated 21 days later. In that trial conducted in adults, most EVD events occurred shortly following vaccination; no EVD events occurred more than 6 days after vaccination. The durability of the effect of the vaccine was not assessed.

Two other vaccines, the GlaxoSmithKline (GSK) ChAd3-EBO Z (replication deficient Chimpanzee adenovirus type 3-derived vector encoding the Ebola virus Zaire [EBO Z] GP) vaccine and the Johnson & Johnson (J&J) prime boost vaccine, rHAd26/MVA, have completed phase 1 testing. In addition, safety and immunogenicity after 12 months of the rVSVΔG-ZEBOV-GP and ChAd3-EBO Z vaccine have been evaluated in a phase 2, placebo-controlled trial of adults in Liberia (Partnership for Research on Ebola Virus in Liberia [PREVAIL] I).

By the end of 2015 in West Africa, the incidence of EVD had dramatically decreased. However, multiple questions regarding the safety and effectiveness of EVD vaccines remain unanswered, including the durability and the immediacy of immune responses generated by different vaccine strategies with and without a booster, and the safety of the different vaccines, particularly in children.

In order to answer these questions, a randomized trial that includes adults and children will be carried out. The trial will compare three vaccine strategies with placebo for immunogenicity and safety. The comparisons will be carried out separately for adults and children and for adults and children combined. The three vaccine strategies are: 1) Ad26.ZEBOV (prime) (0.5 mL) followed by an MVA-BN-Filo boost (0.5 mL) at 56 days; 2) rVSVΔG-ZEBOV-GP (prime) (1 mL) with a placebo (1 mL) boost at 56 days; and 3) rVSVΔG-ZEBOV-GP (prime) (1 mL) with a rVSVΔG-ZEBOV-GP boost (1 mL) at 56 days. There will be two placebo groups, one with a syringe fill volume of 0.5 mL to match the fill volumes of the Ad26.ZEBOV and MVA-BN-Filo vaccines and the other with a fill volume of 1 mL to match the fill volume for the rVSVΔG-ZEBOV-GP vaccine. The two placebo groups will be combined for data analyses.

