## **2.9. Randomization and blinding**

Eligible participants will be randomized in a 2:1:2:1:1 allocation to rHAd26/MVA (prime and boost), 0.5 mL of placebo (prime and boost), rVSV $\Delta$ G-ZEBOV-GP without a boost, rVSV $\Delta$ G-ZEBOV-GP with a boost, or, 1mL of placebo (prime and boost) (Figure 1). Syringes will be pre-labelled with a unique SID number according to a centrally prepared randomization schedule. The tear-off label will also include a bar code identifier. For each vaccination center, the randomization schedule will be prepared using block randomization to ensure the desired allocation ratio for the five arms of the study for each vaccination center.

It is possible that the person carrying out the vaccination will be able to differentiate syringes by the fill volume. The rVSV $\Delta$ G-ZEBOV-GP vaccine has a 1 mL fill volume and the rHAd26/MVA vaccines have a 0.5 mL fill volume. The person carrying out the vaccination will not know whether vaccine or matched placebo is given.

At the time of vaccination, a tear-off label on the syringe that includes the SID will be attached to the baseline CRF (or an eCRF will be used). This will be the primary

link used between the vaccine administered and the PID, and PIDs associated with SIDs will be available to the pharmacy.

With this approach, randomization does not occur until the participant is vaccinated with the prime vaccine.

Participants randomized to the rVSVΔG-ZEBOV-GP vaccine without a boost for the initial vaccination will receive placebo (1.0 mL fill) at 56 days. Those randomized to receive rHAd26/MVA initially will receive the MVA-BN-Filo boost at 56 days in a syringe with a 0.5 mL fill; and those randomized to rVSVΔG-ZEBOV-GP with a boost will receive the rVSVΔG-ZEBOV-GP vaccine again at 56 days in a syringe with a 1 mL fill. Two groups will receive placebo (saline) for the prime and booster vaccination. For one group, a 0.5 mL fill syringe will be prepared for each vaccination and for the other a 1.0 mL fill syringe will be prepared for each vaccination. The syringe used at 56 days will be labeled with the volunteer's PID.

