Prior to carrying out the endpoint analyses which pool the two placebo groups, the two placebo groups will be compared for the immunogenicity and safety outcomes. The primary analyses for adult and children will be carried out at the 0.0167 (2-sided) level of significance and will compare the three vaccine strategies with the pooled placebo group for the percent with a positive antibody response at 12 months. Each pair-wise comparison will be carried out using Mantel-Haenszel chi-square statistics which consider stratification by vaccination center. Similar methods will also be used to compare groups for the immediacy of the antibody response at 14 days. These analyses will exclude those participants with elevated antibody levels at baseline. Participants will not be screened at study entry for elevated antibody levels. These exclusions will be carried out during analysis. Analyses will also be carried out for all randomized participants irrespective of antibody level at baseline.

Similar methods will be used to compare antibody responses of each vaccine strategy with the pooled placebo group at other time points, including 28 days after randomization and 28 days following the booster vaccination. The two additional primary objectives for immune responses, pooled rVSVΔG-ZEBOV-GP groups versus pooled placebo groups 28 days after randomization for Merck, and rHAd26/MVA versus pooled placebo groups approximately 28 days following

booster vaccination for Janssen, will be carried out the 0.05 (2-sided) level of significance.

All comparisons (for adults, children, and for adults and children combined) of immune responses and safety outcomes at other time points will be carried out at the 0.0167 (2-sided) level of significance when there are three pair-wise comparisons made (e.g., each vaccine strategy versus pooled placebo) and at the 0.025 (2-sided) level of significance when there are two pair-wise comparisons made (e.g., for comparisons at days 7, 14, 28 and 56 with the pooled placebo group in which the two rVSVΔG-ZEBOV-GP strategies are pooled).

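### The SAP tests injection-site reactions against a placebo pool of mixed volume, leaves out the protocol's comparison of the two placebos, and makes the matched-placebo contrast optional

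*SAP*

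**What the plan says.** **Protocol.** The synopsis (Background and Rationale) sets up a 0.5 mL and a 1 mL saline group to match the fill volumes of the two products and states: "The two placebo groups will be combined for data analyses". Section 2.4 names the pooled placebo as comparator for injection-site reactions after prime and after boost. Section 7.1 attaches two safeguards. Before any pooled endpoint analysis, "the two placebo groups will be compared for the immunogenicity and safety outcomes". If there is "evidence that safety outcomes differ between the two placebo groups", then "analyses will also be performed for each vaccine versus its matched placebo". The matched analysis is thus conditional, but mandatory once the condition is met, and it is added to the pooled analysis.

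**SAP.** Section 2.1.5.5 states that "proportions will be compared between each vaccine strategy and the pooled placebo using the Mantel Haenszel chi-square test stratified by site"; site is the only stratification factor. On matching it says: "For safety outcomes, comparisons may also be made between each active vaccine and its matching placebo". The same permission is repeated for pain, itching and targeted symptoms. Section 2.1.5.6 carries these methods into the daily diary for children. No section of the SAP compares the two placebo groups with each other or states when the matched contrast would be run. The baseline table (2.1.1) is laid out for four groups, so there too the placebos appear as one.

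**The concern.** Two placebo volumes exist because the two products have different volumes. Local reactions are the outcome on which injected volume could most plausibly act by itself. Each product's own placebo removes such an effect; a half-and-half pool does not. Stratifying by site does not help, because both volumes are randomized at every centre.

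The arm given rVSV without a boost shows the problem clearly. At day 56 it receives 1 mL of saline and is compared with a pool that received 0.5 mL or 1 mL of saline. Apart from any after-effect of the prime, a difference in new local reactions there could reflect volume alone.

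At stake is how the reactogenicity of the two products reads side by side, since any shift has opposite signs for them. Under the SAP as written, a reader of the final report might be unable to tell whether pooling was harmless. An optional contrast with no stated criterion can also be run or left out after results are seen.

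**Working it through.** **Inputs.** Allocation is 2:1:2:1:1 (protocol 2.9). With 1,401 adults and 1,401 children (SAP section 2), each age stratum has about 400 rHAd26/MVA, 600 rVSV (both arms pooled before the boost), 200 on 0.5 mL placebo and 200 on 1 mL placebo. The two-sided level is 0.025 when two comparisons are made (protocol 7.1), so 0.0125 per tail and z = 2.241. Local-reaction rates by placebo volume are in neither document; those below are assumptions.

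**The plan's own figure.** No power is stated for local reactions. The nearest safety figure is 0.88 for SAEs, 5% versus 12%, 400 per group, level 0.0167 (protocol 2.7). The pooled-variance two-proportion formula gives (0.07 − 2.393 × 0.01972)/0.01956 = 1.166, power 0.878. It reproduces, so the same formula is used below.

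**Shift.** Let D = p(1 mL) − p(0.5 mL). With a 1:1 pool, the pooled rate is [p(0.5 mL) + p(1 mL)]/2. Relative to matched placebo, the rVSV difference moves by +D/2 and the rHAd26/MVA difference by −D/2.

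**Wrong decisions.** Suppose a vaccine has exactly its own placebo's rate. The chance that it is declared different from the pool, in the direction of the shift, is Φ[(|D|/2 − z·se0)/se1]. Here se0 uses the overall rate and se1 the two groups' own rates. For rVSV at 10% (1 mL) versus 5% (0.5 mL): the pool is 7.5% and the overall rate (600 × 0.10 + 400 × 0.075)/1000 = 0.09. Then se0 = √(0.09 × 0.91 × (1/600 + 1/400)) = 0.01847 and se1 = √(0.10 × 0.90/600 + 0.075 × 0.925/400) = 0.01798. The result is Φ[(0.025 − 0.0414)/0.01798] = Φ(−0.91) = 0.18.

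**Power of the placebo check.** This is 200 versus 200 per age stratum at 0.05 two-sided, same formula.

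| 1 mL / 0.5 mL rate | Shift (points) | rVSV declared worse than pool | rHAd26/MVA declared better than pool | Power of placebo check |
|---|---|---|---|---|
| 5% / 5% | 0 | 1.25% | 1.25% | – |
| 6% / 5% | ±0.5 | 2.7% | 2.7% | 0.06 |
| 8% / 5% | ±1.5 | 8% | 9% | 0.23 |
| 10% / 5% | ±2.5 | 18% | 22% | 0.48 |
| 20% / 15% | ±2.5 | 10% | 10% | 0.26 |
| 25% / 15% | ±5 | 34% | 35% | 0.71 |
| 25% / 10% | ±7.5 | 72% | 80% | 0.98 |

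If the 0.5 mL saline had the higher rate, the signs would reverse.

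**Price of matching.** With rVSV at 50% and placebos at 25% and 15%, the 95% half-width is 1.96 × √(0.25/600 + 0.20 × 0.80/400) = 5.6 points against the pool. Against the 1 mL placebo it is 1.96 × √(0.25/600 + 0.25 × 0.75/200) = 7.2 points. For a true 12% versus 5% at level 0.025, power falls from 0.91 to 0.71 for rHAd26/MVA (400 versus 400, then 200) and from 0.95 to 0.76 for pooled rVSV (600 versus 400, then 200).

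**The case against.** The other side has four good arguments.

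- **No bias is shown.** Neither document gives a reaction rate by volume or says that volume causes reactions. With equal rates the shift is zero. This stands: the effect is conditional in existence, size and sign.
- **Pooling is the protocol's choice.** Its objectives name the pooled comparator, and its matched analysis only supplements it. This also stands. A reader might infer that the matched placebo should replace the pool for local reactions. The protocol does not support that, and the lost power to detect harm is a real argument against it.
- **The SAP keeps the matched contrast and nowhere withdraws the check.** In addition, protocol 7.1 introduces its list as work done during the trial for the DSMB, so the check may not have been meant for the final report. This stands in part: the safeguard is weakened, not abolished. But 7.1 places the check ahead of the pooled endpoint analyses, and the same section makes the SAP govern final analyses. On either reading, the final report has no planned check.
- **Blinding.** A reader might infer that the pool is an unblinded comparator, since the protocol concedes: "It is possible that the person carrying out the vaccination will be able to differentiate syringes by the fill volume". That sentence concerns only the person injecting. Section 2.9 states that participants and the staff assessing safety are blinded, and nothing says that volume reaches them.

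A reader might also extend the point to systemic symptoms. The documents give no basis for a volume effect there.

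**Conclusion.** The point holds as a gap between protocol and SAP, limited to injection-site reactions. A required comparison of the placebos is absent from the SAP, and a conditional duty has become a discretionary one. The consequence is conditional: a shift of D/2, opposite in sign for the two products, only if the two saline volumes produce different reaction rates. Under the assumed rates it runs from nothing to 7.5 points. At a one-point gap the effect on error rates is small; at gaps of five points or more it is material.

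The figures rest on a 1:1 pool, about 200 per placebo group in each age stratum, the normal approximation, and a vaccine no different from its own placebo. They do not show that the trial's reactogenicity results are biased.

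Restoring only a significance-triggered check would be a weak remedy: in the 10%/5% and 20%/15% cases it would miss the difference more often than not.

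**What to change.** In SAP 2.1.5.5 and 2.1.5.6:

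1. Restore the comparison of the 0.5 mL and 1 mL placebo groups, and report their reaction rates in separate columns.
2. For injection-site reactions (redness, swelling or induration, pain, itching), replace *may* with *will* in the clause "comparisons may also be made between each active vaccine and its matching placebo". Then rVSV versus 1 mL placebo and rHAd26/MVA versus 0.5 mL placebo are always reported beside the pooled comparison, whatever the placebo check shows. The pooled comparison stays the protocol comparator.
3. For systemic symptoms, state the protocol's own rule: matched analyses are run if the placebos differ.

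The cost is wording and extra tables, with no new data. The SAP was written before unblinding, so these contrasts could be fixed without knowledge of results. The matched contrasts have wider intervals and less power, which is why they should sit beside the pooled result and not replace it.
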